Studies such as the Diabetes Prevention Program (DPP), Look AHEAD, and the SHIELD study illustrate a gap in the quality of diabetes care and its effectiveness in improving long term medical outcomes in participants with pre-diabetes and type 2 diabetes (T2DM) (2-5). The DPP has demonstrated that a lifestyle intervention aimed at 7% weight loss and 150 minutes of weekly activity reduced the risk of developing diabetes by 58% over 2.8 years, compared to placebo (2). The Look AHEAD study has compared a program of diabetes support and education to a DPP-adapted lifestyle intervention aimed at 7-10% weight loss and 175 minutes of weekly activity in people with type 2 diabetes and demonstrated significantly greater weight loss (8.6% vs. 0.7%) and fitness after 1 year, resulting in improvements in glycemia, blood pressure, and lipids with simultaneous reductions in medications and costs to treat these conditions (3). Yet SHIELD showed that while participants with type 2 diabetes comprehend the severity of their disease, they lack the skills and decision-making support to make a significant lifestyle change (5). These studies highlight a number of behavioral and lifestyle interventions proven to have positive outcomes on patient quality of life, health measures, and healthcare costs (6,7). Many translation projects of the DPP have been implemented in people with prediabetes (8). However, to our knowledge, the Look AHEAD study, which has completed an 11-year efficacious lifestyle intervention program for participants with type 2 diabetes, has not yet been translated to the clinical practice setting.

We performed a pilot translation for this project called the IDOLc (Improving Diabetes Outcomes through Lifestyle change) study. We randomly assigned 57 MGH primary care participants with T2DM and $BMI > 25 \text{ kg/m}^2$ who were taking at least one non-metformin, non-GLP1 diabetes medication to dietitian referral for medical nutrition therapy (RD-MNT) or a 19-week group lifestyle intervention adapted from the published Look AHEAD curriculum. Participants were 61 years old, 59% male, 32% non-white, and weighed 97 kg with mean HbA1c 8.2%. At 6 months, 46% of group lifestyle vs. 21% of RD-MNT lost $> 5\%$ body weight ($P=0.039$), with mean weight loss 6.6 (SD 7.0) kg with group lifestyle and 2.1 (3.5) kg in RD-MNT ($P=0.004$). Eighty-two percent vs. 38% stopped or reduced diabetes medications

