This project is funded by the National Institutes of Diabetes and Digestive Diseases (NIDDK; grant R18 DK102737, under PAR 12-172, Translational Research to Improve Obesity and Diabetes Outcomes). In addition, it aligns with Partners and MGH's Diabetes Care Redesign initiative, which supported the pilot work under a Clinical Innovation Award to [name], and with MGH's Strategic Plan goal to address obesity in diabetes in the communities MGH serves.

While this project is being funded and conducted as research, it is a true translational effort meant to bridge the gap between what we know to be effective in clinical trials and what is possible in clinical settings. As such, it is a hybrid, with research staff at the MGH Diabetes Center acting as a "coordinating center" for central research activities such as screening and health center provider co-investigators trained and funded to carry out the work in usual care settings. Consequently, there are several novel aspects of this project.

Group conference call arm. Delivering this intervention via group conference call could potentially increase reach by having one central team manage participants across a health system, but it has not yet been attempted. Because this is a novel component, we propose to conduct structured interviews of eligible participants before launch to obtain feedback on the telephone modality and shape the potential use of 3-4 in-person sessions at the beginning of the telephone intervention to increase engagement. The group teleconference intervention will be conducted using "reserved conference calls" in which participants use their own phones to call into the session at a prearranged time using a toll-free number. Participants may apply for reimbursement for excess use of cell phone minutes. There is evidence to support the group telephone delivery

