arm. In the SHINE study, the success of the group telephone delivery of the DPP lifestyle intervention program in achieving comparable weight losses to individual phone-delivered intervention at 1 year, and continued, sustained weight losses at 2 year follow up compared to weight regain in individual phone-delivered intervention in the SHINE study represents exciting innovation, effectiveness, and potential for reach but has not been tested using the Look AHEAD intervention (9). In addition, a large proportion of patient population at the community health centers lack internet access to enable implementation of other novel technologies, but 91% of Americans have telephones (10). The telephone intervention is evidence-based, lower cost, and more convenient for participants than in-person groups as they do not have to travel, increasing reach (11-14).

Role of the community health center primary care clinician leaders and staff. The community health center clinicians will provide logistical and medical oversight to the project, anchoring it at each community health center. [name] and [name] cross-cover their colleagues as members of a practice group; [name] ANP APRN runs the diabetes programs at Chelsea health center, collaborating in the care of patients of all of the physicians and nurse practitioners at her practice (inclusion of a nurse practitioner medical leader in the REAL HEALTH-Diabetes project enhances generalizability and reach). They will promote the project to their colleagues and support recruitment efforts by co-signing recruitment letters (which will be created by Diabetes Center Research personnel). More importantly, they will be the supervising medical care providers for participants in the program. They will be trained by [name] (Co-PI). Community health center staff will be funded by the REAL HEALTH-Diabetes grant for this work.

A final potential benefit to health center participants is the ability to offer the lifestyle program at no cost to its patients and to train staff in cutting edge lifestyle change strategies.

II. SPECIFIC AIMS

a. Objectives and hypotheses to be tested in the research project

The goal of this project is to translate the Look AHEAD intensive lifestyle intervention for type 2 diabetes and obesity into usual care at community health centers, comparing an in-person group program (IP), a telephone conference call (TCC) group program, and referral to medial nutrition therapy (MNT), the current standard of care.

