Aim 1: To evaluate the effectiveness of the REAL HEALTH-Diabetes lifestyle change program comparing in-person (IP) group and telephone conference call (TCC) group intervention to individual dietitian referral for MNT.

H1a. Primary outcome. Weight loss: We hypothesize that the IP and TCC lifestyle groups will demonstrate greater weight loss than MNT at 6 months, and that the lifestyle group participants will have more sustained weight loss at 12, 24 and 36 months. The sample size of 210 provides 80% power to detect a 3.5% difference between any two groups adjusting for three group comparisons, 10% drop-out rate, and intraclass correlation (ICC=0.02).

H1b. Secondary outcomes. Medical outcomes: We hypothesize that compared to individual MNT, participants in the IP and TCC group interventions will maintain or improve HbA1c, blood pressure, and lipids from baseline with reduced medication use

(dose and cost) to treat these conditions, both at the end of the intensive intervention and at follow-up.

H1c. Behavioral and psychosocial outcomes: We hypothesize that compared to MNT, the lifestyle groups will have greater improvements from baseline in health behaviors and the patient-reported outcomes of self-efficacy and health-related quality of life.

Aim 2: To evaluate the reach, adoption, implementation fidelity, and maintenance of the two adapted Look AHEAD lifestyle change programs (IP and TCC) at the three community health centers, comparing factors across centers using the RE-AIM Model Dimension items checklist. We will use a mixed methods approach, first using structured interviews with participants who would be eligible to participate to inform the design of the telephonic intervention, then using provider surveys and participant structured interviews in years 2-4 to assess engagement and adoption by providers and compare responders and non-responders. Participant structured interviews will be conducted when the participant has completed the active intervention at year 2. Structured interviews will be administered by non-blinded study staff, and will follow the same procedures as described for the initial structured interviews that indicate the study design [see V. Study Procedures]. We will also collect quantitative indicators of implementation.

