Aim 3: To estimate the incremental cost per percentage point decrease in body weight of the implementation strategies assessed in this study compared to usual care. The focus of our analysis will be identifying short-term costs and health effects that are relevant to accountable care organizations and insurers with the goal of informing the design of payment contracts that ensure the adoption of effective and efficient diabetes care, with a particular focus on the tradeoffs between costs and effectiveness of telephone compared to in-person format.

III. SUBJECT SELECTION

a) Inclusion/exclusion criteria

Eligibility criteria for participation include:

- Diagnosis of type 2 diabetes
- Age 18 years or older
- Overweight or obese ($BMI > 25 \text{ kg/m}^2$) unless of Asian descent then BMI criterion is lowered to $BMI > 23 \text{ kg/m}^2$
- HbA1c level $6.5 < 11.5\%$
- Systolic blood pressure (SBP) $< 160 \text{ mmHg}$, diastolic blood pressure (DBP) $< 100 \text{ mmHg}$
- Willing to lose 5-7% of body weight
- Willing to increase activity to at least 175 minutes/week
- Willing to commit to random assignment to either attend and participate in the lifestyle change program in person or on the telephone or be referred to Nutrition Services for medical nutrition therapy
- Stable health, with no severe comorbidities that might interfere with their ability to participate in a group intervention that includes increasing activity or decreasing calories, such as severe psychiatric illness or significant heart disease
- Ability to understand and communicate effectively in English or Spanish
- Willing to self-monitor blood glucose
- Willing to keep a food, exercise, and blood glucose diary

- Have a primary care physician at MGH Chelsea, Charlestown, Revere Health Centers, or any Partners affiliated practices or be willing to attend sessions, in-person or by phone, and have medications adjusted by a provider based at one of those health centers or the MGH Diabetes Center with communication to the referring primary care provider

Exclusion criteria include:

- Weight greater than 350 pounds
- Pregnant or planning pregnancy in the next year
- Currently seeing a dietitian (regular scheduled follow up appointments) or participating in a weight loss program and unwilling to stop
- Weight change of more than 3% body weight in the previous 1 month.
- Currently enrolled in another diabetes study
- Lack of availability of telephone

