Participants will be given a calendar to track health service utilization with a particular focus on emergency room visits and hospital admissions outside the Partners system, as these cannot be tracked administratively [See “19. Medication and Health Service Utilization”]. Participants will receive postcard reminders at 3 months to remind them to keep their health service utilization calendar record.

VI. BIOSTATISTICAL ANALYSIS

a. Specific data variables (e.g. data collection sheets)

A list of the variables collected via medical chart review, survey instruments (from screening interview, research visits, RE-AIM components, and cost estimates) are listed in the protocol appendix [see “20. Data variables list”]

b. Study outcomes

All outcomes will be assessed at baseline (prior to randomization) and at 6, 12, 24 and 36 month follow up after completion of the lifestyle intervention program. Primary study endpoint will be change in weight from 0 to 6 months after enrollment in the intervention, with secondary outcomes being weight change at other timepoints, glycemia (HbA1c), blood pressure, and lipids and medication prescriptions (number, dose and cost) for these conditions as well as health behavior, self-efficacy, measures of self-determination, depression, food insecurity, health related quality-of-life, patient satisfaction, and cost.

c. Statistical methods

For all continuous outcomes (% weight loss, HbA1c, blood pressure, fasting lipid levels, self-efficacy, health related quality-of-life score, and satisfaction with care), we will compare changes from baseline among groups using a mixed effects model that includes group, follow-up period (6 months, 1 year, 2 years, 3 years), group and period interaction, baseline weight, and community health center. The follow-up period will be modeled as a categorical variable;

average changes at each time point by treatment group as well as the overall change (with all follow-up visits included in the model) will be presented. Since outcomes from participants within the same counseling group might be correlated, all analyses will take into account the clustering effect in the mixed effect models. With three treatment groups, multiple comparisons adjustment will be applied to reduce the inflation of type I error rate. Randomization codes will be generated for each health center and group assignment will occur in a 1:1:1 ratio within each site stratified by sex.

d. Power analysis

Aim 1:

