Sample size/power calculation.

H1a. IDOLc preliminary data showed 6.7% mean weight loss at 6 months in the lifestyle intervention group, which was 4.1% greater than the MNT group. The standard deviation of percent weight loss in the pilot cohort was 5.5. Our aim is to detect a clinically meaningful 3.5% difference between any of the two study groups (where weight maintenance is defined as weight change <3%⁷¹). We use the conservative Bonferroni method to adjust for 3-arm multiple comparisons, which reduces the two-sided significance level to 0.0167 (0.05/3). Assuming a SD of 5.5%, the study will need an effective sample size of 54 per arm to detect a 3.5% difference with 80% power. We assume a conservative intraclass correlation coefficient of 0.02 within each counseling group, which translates into an inflation factor of 1.2, and 10% drop-out rate based on our prior results and the fact that participants receive primary care at study sites. The final sample size will be 210, 70 per arm.

Further analyses:

H1b. We hypothesize that participants in the group interventions will maintain or improve HbA1c, blood pressure, and LDL with reduced medication use (dose and cost) to treat these conditions, both at the end of the intensive intervention and at follow-up, compared to the MNT arm. Medication reduction is an outcome that is meaningful to participants and reduces costs to payors (40,41). Based on our preliminary data, in which 61% of the lifestyle group had improved HbA1c on less medication compared to 31% in the MNT group, we have 81% power to detect a difference of 33% with an effective sample size of 54 per group, adjusting for the 3-arm comparison. We will perform further analyses employing number of medications, insulin use, insulin doses, and Diabetes Medication System Questionnaire, PAM-D or similar weights to model differences in medication intensity among groups (42,43).

H1c. Using the standard deviation estimates from our previous data (44,45), the study will have 80% power to detect a mean difference of 0.35 (on a scale of 1 to 5) in the change of low-fat diet self-efficacy measure between the two lifestyle change arms or between either lifestyle change and the MNT arm, assuming a standard deviation of 0.55. For the change in exercise self-efficacy measure, the study will have 80% power to detect a mean difference of 0.88 (on a scale of 1 to 7), respectively, assuming a standard deviation of 1.4.

Aim 2:

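### The stated 80% power for 3.5 points between any two groups is not supported for in-person vs telephone: about 54–64% if both arms spread like the pilot lifestyle arm

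*Combined protocol and SAP*

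**What the plan says.** Section II, H1a: "The sample size of 210 provides 80% power to detect a 3.5% difference between any two groups", allowing for three comparisons, 10% drop-out and an intraclass correlation of 0.02. Section VI.d, H1a, repeats the target for any pair of arms, sets the two-sided level at 0.05/3 = 0.0167, and derives 54 effective participants per arm and 210 in total. The only measure of spread is one value: "The standard deviation of percent weight loss in the pilot cohort was 5.5".

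The background section reports the same pilot by arm, in kilograms: "with mean weight loss 6.6 (SD 7.0) kg with group lifestyle and 2.1 (3.5) kg in RD-MNT". No percent-scale SD by arm appears anywhere.

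The telephone arm was not in the pilot. On delivering this intervention by group conference call, the rationale section says "but it has not yet been attempted". It cites a study of group telephone delivery of a different lifestyle programme, "but has not been tested using the Look AHEAD intervention", and gives no SD from it.

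IP vs TCC is one of the three comparisons that the significance level is divided among. It also matters to Aim 3, which looks at short-term costs and effects "with a particular focus on the tradeoffs between costs and effectiveness of telephone compared to in-person format". The Aim 3 cost-effectiveness ratio in section VI.d divides by the difference in average percent weight loss between two models.

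**The concern.** A power statement for any pair needs an SD that is plausible for every pair. In the pilot, the lifestyle arm's SD in kilograms was twice that of the MNT arm. A single value from the combined cohort overstates the spread of one arm and understates that of the other. When a lifestyle arm is compared with MNT, the two errors largely cancel. When two lifestyle arms are compared, no narrow arm brings the average down, and the plan gives no reason to expect 5.5 in both.

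At stake is how an IP vs TCC result is read. Readers would take from sections II and VI.d that this pair had 80% power for 3.5 points.

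**Working it through.** **Inputs.** From section VI.d: difference 3.5, SD 5.5, alpha 0.0167, 54 effective per arm, pilot mean losses 6.7% (lifestyle) and 6.7 − 4.1 = 2.6% (MNT). From the background section: 57 pilot participants, baseline weight 97 kg, mean losses 6.6 and 2.1 kg, SDs 7.0 and 3.5 kg. Arm sizes are not stated. I infer 28 lifestyle and 29 MNT, the split that reproduces the reported pilot percentages (for example 13/28 = 46%, 6/29 = 21%, 23/28 = 82%, 11/29 = 38%).

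**Method.** Two-sample t-test with arm-specific SDs and Welch degrees of freedom. Noncentrality = 3.5 / √(s₁²/n + s₂²/n); power is the probability that the noncentral t exceeds the two-sided critical value.

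**Step 1: the plan's figure.** SE = 5.5 × √(2/54) = 1.058; noncentrality = 3.5/1.058 = 3.31; critical t (106 df) = 2.43; power = 80.7%. The plan's arithmetic is right. Working back from 70 per arm, 70 × 0.9/1.2 = 52.5 effective, with power 79.4%, which is still about 80%.

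**Step 2: what 5.5 resembles.** Pooled pilot SD = √[(27 × 7.0² + 28 × 3.5²)/55] = 5.50 kg, and 5.50/97 = 5.7%. So 5.5 is consistent with an average over one wide and one narrow arm.

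**Step 3: percent SDs by arm.** These must be reconstructed. Four readings (lifestyle / MNT):

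- A. 5.5 is the whole-cohort SD. Total sum of squares 56 × 5.5² = 1694; between arms (28 × 29/57) × 4.1² = 239.5; within-arm SD = √(1454.5/55) = 5.14. Split 2:1 as in kg: MNT = 5.14 × √(55/(27 × 4 + 28)) = 3.27, lifestyle 6.54.
- B. 5.5 is the within-arm SD, split 2:1: MNT = 5.5 × √(55/136) = 3.50, lifestyle 7.00.
- C. Kilograms over 97 kg: 7.22 / 3.61.
- D. Each arm scaled by its own percent-to-kg ratio of means: 7.0 × 6.7/6.6 = 7.11; 3.5 × 2.6/2.1 = 4.33.

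**Step 4: power at 54 effective per arm.**

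| Reading | Lifestyle / MNT SD | IP vs TCC, both at lifestyle SD | IP vs TCC, TCC SD 5.5 | Lifestyle vs MNT | IP vs TCC difference detectable at 80% |
|---|---|---|---|---|---|
| A | 6.54 / 3.27 | 63.6% | 71.7% | 85.5% | 4.13 |
| B | 7.00 / 3.50 | 56.8% | 67.5% | 79.8% | 4.42 |
| C | 7.22 / 3.61 | 53.7% | 65.5% | 76.9% | 4.56 |
| D | 7.11 / 4.33 | 55.2% | 66.5% | 74.1% | 4.49 |

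Example, reading C: SE = 7.22 × √(2/54) = 1.389; noncentrality = 3.5/1.389 = 2.52; power 53.7%. At 52.5 effective per arm the IP vs TCC column becomes 52–62%. For 80% power at 54 per arm, a common SD can be no larger than about 5.54.

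**The case against.** **The hypothesis itself is little affected.** H1a predicts that IP and TCC each beat MNT; it predicts no IP–TCC difference. This stands. Power for those contrasts straddles 80%, and at the pilot's own 4.1-point difference the four readings give 88–95%. A reader might infer that the trial is underpowered for its primary hypothesis. The documents do not support that.

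**The percent SDs are reconstructed.** True, and the kg and percent figures fit together imperfectly: 6.6 kg at 6.7% implies about 98 kg, while 2.1 kg at 2.6% implies about 81 kg, averaging about 89 kg against the reported 97. With 5.5 as the equally weighted pooled SD, an SD ratio of 1.5:1 instead of 2:1 gives 65% power for IP vs TCC, and 1.25:1 gives 71%. The size of the shortfall is therefore uncertain, though none of these reaches 80%.

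**The pilot does not exclude 5.5.** Also true. Chi-square 95% limits for an SD from 28 patients run from 5.2 to 9.8 across the readings, or about 86% down to 28% power. Those limits assume normality, which fits poorly: with mean 6.7 and SD 6.5–7.2, about 60% should have lost more than 5%, against the 46% reported. A few large losses may drive the 7.0 kg. It would be too strong to say that IP vs TCC power is known to be below 80%.

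**The planned analysis is not an unadjusted t-test.** Section VI.c uses a mixed model with baseline weight and health center, which could reduce residual variance. Restoring 80% would need those covariates to explain about 28–41% of it; the documents quantify no such gain. Section VI.c also leaves the multiplicity method open ("multiple comparisons adjustment will be applied to reduce the inflation of type I error rate"). Even if a procedure allowed this pair to be tested at 0.05, power would be 70–79%.

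**Two further inferences should not be drawn.** One is that the sponsor intends to present a null IP vs TCC result as equivalence: no section plans this, and the Aim 3 part of VI.d says that cost outcomes are not powered. The other is that the analysis model is mis-specified: section VI.c never states a common residual variance, and it already ties clustering to the counselling group.

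**Conclusion.** The concern holds as a point about a stated power figure. The 80% claim is about right for lifestyle vs MNT (74–86%). For IP vs TCC, 5.5 is not supported as the planning SD. The pilot's best estimates put power at about 54–64% if both arms spread like the pilot lifestyle arm, with 4.1–4.6 points detectable at 80%, and at about 66–72% if the telephone arm has SD 5.5.

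This rests on an inferred 28/29 pilot split, percent SDs rebuilt from kilogram figures, an assumed TCC SD, and an unadjusted comparison at 54 effective per arm and alpha 0.0167. Confidence is medium: the direction is the same in all four readings, but the amount is not settled by the documents.

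**What to change.** In section II (H1a) and section VI.d (H1a):

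- limit the 80% statement to lifestyle vs MNT, worded as about 80%;
- state power for IP vs TCC separately, computed from the pilot lifestyle-arm percent SD, which the sponsor should be able to obtain from the pilot data, with the assumed TCC SD and a sensitivity range;
- say whether 5.5 is a within-arm or a whole-cohort SD.

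This is a change of wording plus a short calculation. It needs no extra participants, no design change and no change to the analysis model. The only downside is a less favourable stated power for IP vs TCC.

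### The H1b power statement uses medication-reduction rates from a pilot in which everyone took a qualifying diabetes drug; this trial has no drug criterion, and the pilot difference was 30 points, not 33

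*Combined protocol and SAP*

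**What the plan says.** Section VI.d (Power analysis, H1b) starts from the IDOLc pilot, where "61% of the lifestyle group had improved HbA1c on less medication compared to 31% in the MNT group". It concludes that "we have 81% power to detect a difference of 33% with an effective sample size of 54 per group", after adjustment for the three-arm comparison. The H1a paragraph of the same section sets that adjustment as Bonferroni, a two-sided level of 0.0167.

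The background section describes the pilot participants as people "who were taking at least one non-metformin, non-GLP1 diabetes medication".

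Section III.a for this trial begins with "Diagnosis of type 2 diabetes" and adds age, BMI, HbA1c, blood pressure, willingness and stable-health conditions. Neither the inclusion nor the exclusion list requires a diabetes drug. H1b does not mention this difference from the pilot. It defines no analysis population by baseline medication, and the model in Section VI.c is specified for continuous outcomes only.

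**The concern.** The outcome behind the H1b power figure has two parts: HbA1c must improve and diabetes medication must go down. In the pilot everyone had a drug that could be cut. In this trial a person with type 2 diabetes and HbA1c in range is eligible on diet alone. Such a person cannot meet the second part, whatever the arm. If all participants are analysed, each one pulls both arms' response rates toward zero and narrows the gap between them.

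The same sentence has a second weakness. The difference it says can be detected is larger than the one the pilot observed, so there is no margin to absorb any dilution.

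At stake is the reading of a null result on this outcome. It could mean that the programme does not reduce medication, or that too few participants had medication to reduce. Choosing a medicated subset after seeing the data would be open to challenge.

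**Working it through.** **Inputs**
- Pilot rates 61% (lifestyle) and 31% (MNT), a difference of 30 points: Section VI.d, H1b.
- Stated power 81% for 33 points, effective n = 54 per arm: same place.
- Two-sided alpha 0.05/3 = 0.0167, so z = 2.394: Section VI.d, H1a.
- Drug-free share u: not in the documents. Assumed 0, 10% and 20%.

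**Step 1: reproduce the 81%.** Take the pilot MNT rate plus 33 points, 64% vs 31%. The normal-approximation power is

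Φ{ [d − c − z·√(2p̄(1−p̄)/n)] / √[(p1(1−p1)+p2(1−p2))/n] },

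with c = 0 (uncorrected) or c = 1/n (continuity-corrected). Here d = 0.33, p̄ = 0.475, and the two standard errors are 0.0961 and 0.0907.
- Uncorrected: (0.33 − 2.394 × 0.0961)/0.0907 = 1.10, power 86.5%.
- Corrected: subtracting a further 1/54 = 0.0185 gives 0.90, power 81.5%.
- Fisher exact, by full enumeration: 81.2%.

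Fisher and the corrected formula both reproduce the plan's figure. Placing the 33 points as 61% vs 28% gives much the same (Fisher 81.6%).

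**Step 2: use the pilot's own difference.** For 61% vs 31%, p̄ = 0.46 and the standard errors are 0.0959 and 0.0915. Uncorrected: (0.30 − 2.394 × 0.0959)/0.0915 = 0.77, power 78%. Fisher: 71%.

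**Step 3: add drug-free participants.** If a share u cannot respond and the rest respond at the starting rates, each arm's rate is multiplied by (1 − u), with n still 54.

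| u | from 64/31: rates | Fisher (uncorrected z) | from 61/31: rates | Fisher (uncorrected z) |
|---|---|---|---|---|
| 0 | 64.0 vs 31.0 | 81% (86%) | 61.0 vs 31.0 | 71% (78%) |
| 10% | 57.6 vs 27.9 | 71% (78%) | 54.9 vs 27.9 | 60% (68%) |
| 20% | 51.2 vs 24.8 | 60% (67%) | 48.8 vs 24.8 | 50% (58%) |

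**Step 4: restrict to participants on any diabetes drug.** The rates stay at 61% vs 31% and n becomes 54(1 − u), ignoring the slightly smaller clusters.
- u = 10%: n = 48.6. Uncorrected z 73%; Fisher with 48 per arm 66%.
- u = 20%: n = 43.2. Uncorrected z 66%; Fisher with 43 per arm 58%.

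Each is better than its all-participant counterpart in Step 3 (68% and 60%; 58% and 50%), although fewer people are analysed. Steps 3 and 4 assume that every medicated participant, including those on metformin or a GLP1 drug alone, responds at the pilot rates.

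**The case against.** The strongest reply is that the sentence is conditional: it gives power for a 33-point difference, and for that difference it is right. With 33 points held fixed, a lower control rate would even raise power (Fisher 85% at 53% vs 20%). This stands. A reader might infer that the 81% is a calculation error, and it is not. What lacks support is the expectation of 33 points, since the pilot found 30 and found them in a medicated population.

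Second, the documents show who may enrol, not who does. The drug-free share could be small. This also stands, which is why the losses above are conditional.

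Third, a reader might go further and treat everyone who would have failed the pilot's drug criterion as a certain non-responder, then restrict the analysis to that criterion. The documents do not support this, because metformin or a GLP1 drug can also be reduced. The narrower restriction can cost power. Suppose 80% meet the pilot criterion and the rest respond at half the pilot rates. The all-participant multiplier is 0.8 + 0.2 × 0.5 = 0.9, giving 68% (uncorrected z), against 66% in the narrow subset. With 60% meeting it, the figures are 58% and 51%.

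Finally, the outcome is one of many unranked secondary outcomes. Other medication measures (number, dose, cost) cover blood pressure and lipid drugs too, and drug-free participants contribute to those. The cost-effectiveness ratio in Section VI.d uses total cost and percent weight loss, not this response rate. Broad eligibility also suits a translational trial. All of this limits the importance of the point. None of it supplies a basis for 33 points in this population.

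**Conclusion.** The concern holds for the basis of the power statement, not its arithmetic. The pilot supports 71% to 78% power at its own difference, depending on the test, before the change in eligibility is considered. Drug-free participants lower this further. At an assumed 10% or 20% share, Fisher power from the pilot rates is 60% or 50%; starting from the plan's 33 points it is 71% or 60%. These figures rest on the assumed share, on zero response among drug-free participants (which follows from the outcome's definition) and on pilot rates in everyone else (which is an assumption).

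A reader might infer that the trial is known to be badly underpowered for H1b. The documents do not support that, because they do not give the baseline medication mix. The primary weight-loss comparison and its sample size are unaffected.

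**What to change.** In H1b, define the analysis population for the combined HbA1c-and-medication response as participants taking any diabetes medication at RV1, and report the all-participant result alongside. Randomisation takes place at the end of RV1, so the subset is defined by a pre-randomisation variable and the comparison stays randomised. Medications are already recorded at that visit (Section V, Aim 1 measures; Table 2).

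Replace the 81% statement with power at the pilot's 30-point difference for the expected number in that subset, over a stated range of the drug-free share, and name the test used.

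The cost is a change of wording, a smaller analysed number and a less favourable stated power for one secondary outcome. Enrolment criteria, the primary endpoint and the sample size of 210 stay as they are.
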